#### Normal or adaptive symptoms

Transient symptoms such as end-of-day dryness, lens awareness, itching or burning or other discomfort may occur with contact lens wear and may occasionally reduce wearing time. **These are not reported as adverse events unless in the investigator's opinion they are unexpected in nature, severe or have a high rate of occurrence.**

This clinical study will also ascertain satisfaction or preference with subjective attributes such as comfort, vision, or lens handling. Responses to these subjective questionnaires will not be considered as Adverse Events.

## 8.2 Procedures for Adverse Events

Treatment of an adverse event will depend on its nature and severity. Based on the clinical judgment of the investigator the subject may be referred to an ophthalmologist for treatment. The investigator will attempt to determine whether the reaction is related to the test device or a result of other factors. An Adverse Event Form (Appendix 1) will be completed for each adverse event. Whenever possible, the adverse event will be photo-documented.

Expenses incurred for medical treatment as part of study participation will be paid by the Sponsor (bills and prescription receipts kept). The subject must be followed until resolution and an Adverse Event Outcome Form (Appendix 1) completed indicating the course of treatment and resolution of the condition.

### 8.3 Reporting Adverse Events

---

All potential Serious and Unanticipated Adverse Device Effects that are related or possibly related to subject participation will be reported to the Principal Investigator and the Sponsor within 24 hours of the investigator becoming aware of the event. The Principal Investigator will report the event to the IRB as soon as possible (by fax, mail/delivery, phone, or email). All fatal or life threatening events will be reported immediately to the IRB.

Significant and Non-Significant Adverse Events will be reported to the Sponsor as soon as possible, but no later than 5 working days after the occurrence.

Sponsor contact details are:

Contact: [REDACTED]

Email: [REDACTED]

Phone: [REDACTED]

Address: [name]

Suite 1

[name]

### 8.4 Discontinuation from the Study

---

A subject's study participation may be discontinued at any time if, in the opinion of the Sponsor or the investigator, it is in the best interest of the subject. All discontinuations will be fully documented on the appropriate study forms and a discontinuation/exit form will be completed.

### 8.5 Device Deficiencies

---

A device deficiency means the inadequacy of a medical device with respect to its identity, quality, durability, reliability, usability, safety or performance. *Any device deficiency that will cause or contribute to a Serious Adverse Event should be reported to the Principal Investigator and the Sponsor within 24 hours of the investigator becoming aware of the deficiency.*

Other defective lenses should be reported to the Sponsor as soon as possible.

This clinical study will also ascertain satisfaction or preference with subjective attributes such as comfort, vision, or lens handling. Responses to these subjective questionnaires will not be considered as complaints or Device Deficiencies.

## 9 Statistical Design and Analysis

---

### 9.1 Statistical Hypothesis

---

The primary statistical hypothesis is that the comfort performance with the Test lens will demonstrate statistical equivalence to the comparator (Control) lens over two days of lens wear.

The secondary statistical hypothesis is that the vision performance with the Test lens will demonstrate statistical equivalence to the comparator (Control) lens over two days of lens wear.

*Other hypotheses:*

The lens fit performance with the Test lens will demonstrate statistical equivalence to the comparator (Control) lens over two days of lens wear.

The lens handling performance with the Test lens will demonstrate statistical equivalence to the comparator (Control) lens over two days of lens wear.

Corneal staining performance with the Test lens will demonstrate statistical equivalence to the comparator (Control) lens over two days of lens wear.

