## 1 Study Objective

---

This is a confirmatory Design Validation study to provide supportive evidence to demonstrate that the [REDACTED] lens meets the clinical performance requirements specified in the User Requirements Design Inputs per D28298, DHF0122.

Specifically, the User Requirements to be evaluated in this clinical study are:

- Vision of [REDACTED] is equivalent to [REDACTED]
- Comfort of [REDACTED] is equivalent (or better) to [REDACTED]
- Lens fit of [REDACTED] is equivalent to [REDACTED]
- Lens handling of [REDACTED] is equivalent to [REDACTED]
- Ocular health of [REDACTED] is equivalent to [REDACTED]

Details of the statistical hypothesis that are required to be met in fulfilment of Validation can be found in Section 9.1 below.

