**Table 1: Study lenses**

	Test Lens	Control Lens
Device Name	[REDACTED]	[REDACTED]
Regulatory status	Investigational	Investigational
Manufacturer	CooperVision, Inc	CooperVision, Inc
Material	rioofilcon A (+ DAB)	rioofilcon A
Water Content (%)	58	58
Base curve (mm)	8.60	8.60
Diameter (mm)	14.10	14.00
Power range (D)	-1.00 to -6.00	-1.00 to -6.00
Label	Investigational [Masked]	Investigational [Masked]

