## **4 Justification for the Study Design**

---

The Apollo lens has successfully passed the preclinical biocompatibility tests as identified in the risk assessment document. Preliminary safety and clinical performance of the [REDACTED] lens have been evaluated in one feasibility clinical study. This study is summarized in the Investigator Brochure (IB).

A two-day crossover study is sufficient to validate the clinical performance of the lens against the User Requirements. A crossover design has been chosen since it minimizes the impact of potential sympathetic effects between the two eyes (e.g. an uncomfortable lens in one eye may impact the subjective rating of the fellow eye). The study contact lenses do not alter the physiology of the eye and hence there is no carryover effect requiring a washout period. The order effect will be tested.

The choice of comparator product was made in order to assess the clinical performance against a currently marketed product representative of generally accepted state of the art.

The choice of study design was made to demonstrate statistical equivalence to the comparator (Control) lens over two days of lens wear. A sample size determination was made of sufficient magnitude so as to be able to adequately test the primary statistical hypothesis, and is shown in Section 9.2.

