### 7.5.2 Visit 1b: Pair 1 Dispensing Visit

*Dispensing visit should occur on same day as Visit 1a. In the event of unacceptable short-term slit-lamp findings, e.g. excessive corneal staining, Visit 1b may be conducted on a different day to Visit 1a, where slit lamp biomicroscopy should be conducted again to confirm eligibility.*

- The first study pair of contact lenses will be selected by the investigator according to the randomization table (Appendix 3) for insertion by the subjects. Subjects will be dispensed the lens power nearest to their vertex corrected refractive error requirement. The lens powers of Pair 1 and Pair 2 will be matched.
- Lenses should be allowed to settle for 10 minutes.
- An initial fit assessment will be made to ensure lens fit is acceptable (Y/N). The subject should be discontinued and exited if the lens fit is found unacceptable and the primary reason for poor fit recorded on the CRF and video footage of the fit collected.
- Monocular spherical over-refraction (SOR) will be conducted to determine if a different lens power is required.
- Monocular and binocular **HIHC** and **HILC** distance logMAR visual acuities will be recorded (SOR will be used if the subject is wearing monovision).
- Final lenses will be inserted and allowed to settle for a further 10 minutes, if applicable.
- Subjective responses will be collected per the Post-Settling Questionnaire (Appendix 4), including:
  - Lens insertion
  - Comfort satisfaction & comfort rating (6-point Likert & 100-point scales)
- A gross assessment of lens surface will be made:
  - Overall lens surface quality/wettability (acceptable / unacceptable)
  - Comments, if applicable

- Lens fit will then be assessed and graded according to the guidelines detailed in CVI Grading scales (see Appendix 2).
  - Lens centration (0.1mm steps)
  - Corneal coverage (Yes / No / Borderline)
  - Post-blink movement (0.1mm steps)
  - Mobility rating (0.50 steps)
  - Overall lens movement (-2 to +2 scale)
  - Overall lens fit acceptance and investigator reason, if unacceptable (0.25 steps). Video will be recorded in the event of poor fit.
- Information for Safety for contact lens wear during the clinical study as described in the section 5.6 will be reviewed with each subject.
- The subject must have a minimum of 8 hours of exposure in the lens on at least 2 days before their next study visit.
- The subject will be dispensed adequate lenses (including spares) to last them until the next study visit.

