### 7.5.3 Visit 2: Pair 1 Follow-up Visit 2 days (+2 days) & Pair 2 Dispensing

*Subjects will be asked to wear lenses for at least 3 hours prior to the visit appointment.*

- The following information will be collected from the subject by the investigator:
  - Wear time at visit (hours).
  - Time of insertion and removal daily since last visit, (to calculate average time and maximum wear time (hours)).
  - Time of day lenses become uncomfortable, if at all, i.e. average comfortable wear time (hours).
- Subjective responses will be collected per the Follow-up Questionnaire (Appendix 5), including:
  - Overall satisfaction (6-point Likert & 100-point scales)
  - Comfort & comfort rating (6-point Likert & 100-point scales)
  - Comfort (insertion) (6-point Likert & 100-point scales)
  - Comfort (end of day) (6-point Likert & 100-point scales)
  - Dryness (freq/severity/bothersomeness) (5-point Likert scales)
  - Stinging/burning (freq/severity/bothersomeness) (5-point Likert scales)
  - Itchiness (freq/severity/bothersomeness) (5-point Likert scales)
  - Scratchy/gritty (freq/severity/bothersomeness) (5-point Likert scales)
  - Lens movement/awareness (freq/severity/bothersomeness) (5-point Likert scales)
  - Handling (6-point Likert & 100-point scales)

- Insertion (freq/severity/bothersomeness) (5-point Likert scales)
  - Removal (freq/severity/bothersomeness) (5-point Likert scales)
  - Lens holding/handling (freq/severity/bothersomeness) (5-point Likert scales)
- Vision (6-point Likert & 100-point scales)
  - Driving at night (6-point Likert & 100-point scales)
- Monocular and binocular **HIHC** and **HILC** distance logMAR visual acuities will be recorded (SOR will be used if the subject is wearing monovision).
- A gross assessment of lens surface will be made:
  - Overall lens surface quality/wettability (acceptable / unacceptable)
  - Comments, if applicable
- Lens fit will then be assessed and graded according to the guidelines detailed in CVI Grading scales (see Appendix 2).
  - Lens centration (0.1mm steps)
  - Corneal coverage (Yes / No / Borderline)
  - Post-blink movement (0.1mm steps)
  - Mobility rating (0.50 steps)
  - Overall lens movement (-2 to +2 scale)
  - Overall lens fit acceptance and investigator reason, if unacceptable (0.25 steps). Video will be recorded in the event of poor fit.
- The subject will remove the study lenses which will be retained for return to the Sponsor.

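### Comfort must be equivalent or better under section 1, but the Validation hypothesis in section 9.1 is plain equivalence, and section 9.3 does not say which result decides

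*Combined protocol and SAP*

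**What the plan says.** Section 1 lists five User Requirements. Vision, fit, handling and ocular health are each to be equivalent to Control. Comfort alone is to be such that Test "is equivalent (or better) to" Control. The section then gives the place of the binding criterion: "Details of the statistical hypothesis that are required to be met in fulfilment of Validation can be found in Section 9.1 below".

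Section 9.1 states the primary hypothesis as follows: "the comfort performance with the Test lens will demonstrate statistical equivalence to the comparator (Control) lens over two days of lens wear". It uses the same form of words for vision, fit, handling and corneal staining, so the allowance for a better result is gone. Section 4 agrees with section 9.1: "The choice of study design was made to demonstrate statistical equivalence to the comparator (Control) lens over two days of lens wear".

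Section 9.3 says that equivalence testing will establish non-inferiority first and equivalence afterwards where applicable, in order to confirm the primary and secondary hypotheses. It does not define when equivalence is applicable, gives no margin, and does not say whether non-inferiority alone confirms the comfort hypothesis.

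**The concern.** Equivalence is bounded on both sides. A lens that is sufficiently more comfortable than Control breaches the upper bound and fails, although it satisfies section 1. Section 1 delegates the Validation decision to section 9.1, so the narrower wording is the one that binds.

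Comfort is the sole primary endpoint of a study described as confirmatory. Two outcomes are at risk. A lens that meets the User Requirement could be recorded as failing it. And, because section 9.3 leaves the deciding step open, the choice between the two criteria could be made after the results are known. The second risk exists even if the lenses do not differ.

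**Working it through.** **1. The plan's own figure.** Section 9.2.1 gives n = 44 for a paired t-test, alpha 0.05, SD of the paired difference 13, difference 7. Target power is only called adequate. The noncentral t distribution (df 43, noncentrality 7/(13/√44) = 3.57) gives 93.7% power two-sided, so the statement is consistent. That calculation is for detecting a difference. It does not supply an equivalence margin, and the present point does not rest on it.

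**2. Inputs for the illustration.**
- n = 45 completers (section 7.3) and SD 13 (section 9.2.1).
- Alpha 0.05 for each one-sided test. This is an assumption, because sidedness is not stated.
- Margin M = 7, with 5 and 10 as the range. This is an assumption, because no margin is stated.
- True Test advantage δ of 0, 1, 3 and 5 points. This is an assumption.

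**3. Pass regions.** Let d be the observed mean of Test minus Control and s the observed SD.
- Non-inferior: d > −M + 1.680·s/√45.
- Equivalent: the above, and also d < M − 1.680·s/√45.
- Significantly better (two-sided 0.05): d > 2.015·s/√45.

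The equivalence region lies inside the non-inferiority region. At the same margin and alpha, equivalence therefore never passes a result that non-inferiority fails.

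**4. Cut-offs at s = 13.** The standard error is 13/√45 = 1.938. Significantly better begins at 2.015 × 1.938 = 3.91. Equivalence fails above M − 1.680 × 1.938 = M − 3.26, which is 1.74, 3.74 and 6.74 at margins 5, 7 and 10. At margins 5 and 7, every significantly better result would fail equivalence. At margin 10 this happens only above 6.74.

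**5. Pass rates.** Non-inferiority power comes from the noncentral t with noncentrality (M + δ)/1.938. Equivalence power averages Φ((c − δ)/1.938) − Φ((−c − δ)/1.938) over the distribution of s, with c = M − 1.680·s/√45, counting zero where c ≤ 0. As a hand check with s fixed at 13, M = 7 and δ = 3: Φ(0.74/1.938) − Φ(−6.74/1.938) = Φ(0.38) − Φ(−3.48), about 65%.

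| Margin | Result | δ = 0 | +1 | +3 | +5 |
|---|---|---|---|---|---|
| 5 | Equivalence | 63% | 57% | 26% | 5% |
| 5 | Non-inferiority | 81% | 92% | 99% | >99% |
| 7 | Equivalence | 94% | 91% | 65% | 26% |
| 7 | Non-inferiority | 97% | 99% | >99% | >99% |
| 7 | Significantly better, yet not equivalent | 1.7% | 5.5% | 28% | 67% |
| 10 | Equivalence | >99% | >99% | 97% | 81% |
| 10 | Non-inferiority | >99% | >99% | >99% | >99% |

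At one-sided 0.025 and margin 7, equivalence passes 88%, 84%, 52% and 17%, and non-inferiority 94%, 98%, >99% and >99%.

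**6. An alternative meaning of the requirement.** If equivalent or better means equivalent, or else significantly better, the pass rates at margin 7 are 96%, 97%, 93% and 94%. At margin 5 they are 65%, 64%, 58% and 76%. Plain equivalence falls below this reading too, but at margin 5 this reading differs sharply from non-inferiority (58% against 99% at +3).

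**The case against.** The strongest defence is that section 9.3 already handles the matter. On this view the non-inferiority step serves the or-better allowance, and equivalence follows only where the requirement calls for it. Both results would be produced, together with a paired t-test of subjective scores, so a better lens would be visible in the report. The reading is plausible, but the text does not establish it. The same sequence governs vision, whose requirement in section 1 is plain equivalence. If the sentence makes non-inferiority sufficient for comfort, it does so for vision as well, against section 1. If it does not do so for vision, nothing says that it does for comfort.

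A second defence is that the practical effect is small, and for close lenses with a margin of about 7 or more this stands. Two related inferences do not.
- A reader might infer that the documents expect no comfort advantage. Table 1 does show the same water content and base curve and a closely related material, but also a different diameter, and section 3.1 describes a modified material and design. The documents make no prediction either way; the feasibility results are in the Investigator Brochure.
- A reader might also infer that plain equivalence is safe because it cannot pass a worse lens. It can: the test is symmetric, so at margin 7 it passes a lens truly 1 point worse 91% of the time and one 3 points worse 65% of the time. The supportable statement is the narrower one in step 3.

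A third objection is that section 1 reports requirements from a separate design-input document, which may define the allowance. That stands, and it shapes the fix.

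**Conclusion.** The inconsistency is real. Section 1 allows a better comfort result, the hypothesis it names for Validation does not, and section 9.3 leaves the deciding result unstated. The consequence runs one way only, against the Test lens.

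Its size depends on a margin the plan does not give. With an assumed margin of 7, the loss from requiring equivalence is 3 percentage points at no true difference, 8 at +1, and more than 34 at +3. It is larger at margin 5 and, up to +3, small at margin 10. These figures are illustrations that rest on the plan's SD of 13, 45 completers and one-sided 0.05.

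A reader might go further and conclude that the plan will fail a better lens, or that the 7 points in section 9.2.1 is the margin. The documents support neither: section 9.3 may be applied so that non-inferiority is enough, and 7 points is described only as a difference to detect. The weight is minor to should-fix: a modest wording defect, but on the primary endpoint and cheap to repair.

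**What to change.** Before unmasking:

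1. Check the User Requirements document cited in section 1 for the meaning of the or-better allowance.
2. Restate the comfort hypothesis in section 9.1, and the matching sentence in section 4, so that they carry that allowance.
3. In section 9.3, state that for comfort Validation is decided by non-inferiority: the lower confidence bound of mean Test minus Control lies above minus the prespecified margin. Equivalence is then tested in sequence as a further claim on which Validation does not depend. For vision, state that equivalence is required.
4. If the source document defines the allowance differently, for example as equivalent or significantly superior, use that definition in sections 9.1 and 9.3 instead.

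The cost is wording in three sections, with no change to visits or data. At a given margin and alpha, non-inferiority needs no more subjects than equivalence: at margin 7, no true difference and one-sided 0.05, 90% power needs 31 against 39. Whether 45 is enough still depends on the unset margin; at margin 5 and one-sided 0.025, non-inferiority power at no true difference is only 71%. Leniency towards a worse lens hardly changes: at margin 7 (one-sided 0.05) and a lens truly 2 points worse, non-inferiority passes 81.5% and equivalence 81.3%.

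The downside is that the required comfort claim becomes non-inferior rather than equivalent. The missing margin, the choice among the several comfort ratings, the sidedness of alpha and the multiplicity adjustment are separate gaps, which this change does not close.

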### **5.2 Anticipated Adverse Device Effects**

---

Ocular complications that may occur during the wearing of contact lenses include discomfort, dryness, aching or itching eyes, excessive tearing, discharge, hyperemia and variable or blurred vision. More serious risks may include photophobia, iritis, corneal edema or eye infection. Although contact lens-related infections are very infrequent, the possibility does exist. The incidence of infection due to daily-wear soft lenses is 0.035%. Almost always an infection will occur only in one eye. This risk is assumed by 35-million Americans who currently wear contact lenses.

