## 7.1 Study Endpoints

---

The primary endpoint is:

- Comfort

The secondary endpoints are:

- Vision
- Lens fit
- Lens handling
- Anterior ocular health

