- Slit lamp biomicroscopy will be assessed according to the guidelines set out in the CVI Grading scales (Appendix 2)
- Subjects will undergo washout with saline solution.

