## **9.3 Statistical Analysis**

---

Summary statistics [may/will] be produced (e.g. mean, standard deviation). Paired t-test will be used to compare slit lamp biomicroscopy, lens fit and subjective scores between study lens types. Where applicable, Repeated Measures Analysis of Variance (ANOVA) or paired analysis will be used to compare the variables between study visits. The critical alpha level for statistical significance will be set at  $p \leq 0.05$ , with adjustment for multiple comparisons.

Equivalence testing will be undertaken to first determine statistical non-inferiority and then equivalence (if applicable) to the comparator (Control) lens, to confirm the primary and secondary hypotheses.

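### Equivalent ocular health is a User Requirement, but the only hypothesis for it is corneal staining, and Section 9.3 describes no equivalence test even for that sign

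*Combined protocol and SAP*

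**What the plan says.** All references are to the combined protocol and SAP.

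- **Section 1** lists five User Requirements: vision, comfort, lens fit, lens handling and ocular health, each to be equivalent to the Control (comfort may also be better). It continues: "Details of the statistical hypothesis that are required to be met in fulfilment of Validation can be found in Section 9.1 below".
- **Section 7.1** gives "Anterior ocular health" as a secondary endpoint, and the synopsis lists it as a secondary outcome.
- **Section 9.1** names comfort as the primary hypothesis and vision as the secondary one. Three more follow under a separate label for other hypotheses: lens fit, lens handling and "Corneal staining performance with the Test lens will demonstrate statistical equivalence to the comparator (Control) lens over two days of lens wear".
- **Sections 7.5.3 and 7.5.4** have slit lamp biomicroscopy graded on the Appendix 2 scales at Visits 2 and 3.
- **Section 9.3** says "Paired t-test will be used to compare slit lamp biomicroscopy, lens fit and subjective scores between study lens types". A separate paragraph describes testing for non-inferiority and then equivalence, and ties it to the primary and secondary hypotheses.
- **Section 9.2** sizes the study for comfort and vision only.
- **Section 4** states: "A two-day crossover study is sufficient to validate the clinical performance of the lens against the User Requirements".

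**The concern.** Four of the five requirements have a hypothesis under their own name. Ocular health alone is narrowed to a single sign, and no section says that staining stands for the whole or why. The protocol elsewhere treats the eye's response as wider than staining: Section 5.2 lists "discomfort, dryness, aching or itching eyes, excessive tearing, discharge, hyperemia and variable or blurred vision" among the possible complications and adds corneal edema as a more serious one.

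What is at stake is the wording of the Validation conclusion. A report could state that ocular health is equivalent on the strength of a staining result, with non-significant t-tests on the other signs as apparent support. Neither would justify that statement. For staining itself, the analysis section does not describe the equivalence test that the hypothesis calls for.

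**Working it through.** The plan gives no margin, SD, sample size or power for any ocular-health sign, so there is no figure of its own to reproduce. The first step is to set the sections side by side.

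| User Requirement (Section 1) | Hypothesis (Section 9.1) | Label in 9.1 | Within the equivalence testing of 9.3? |
|---|---|---|---|
| Comfort | Comfort | Primary | Yes |
| Vision | Vision | Secondary | Yes |
| Lens fit | Lens fit | Other | Not on the 9.1 labels |
| Lens handling | Lens handling | Other | Not on the 9.1 labels |
| Ocular health | Corneal staining only | Other | Not on the 9.1 labels |

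Ocular health is the only row where the hypothesis is narrower than the requirement. It also shares the second gap: the only between-lens analysis described for slit lamp findings is the paired t-test.

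**What a non-significant t-test would show.** Inputs: n = 45 completers (Section 9.2.2); alpha 0.05 (Section 9.3, taken as two-sided because sidedness is not stated). Assumed: normal paired differences, and a true worsening of d standard deviations of the paired difference. The test statistic is then noncentral t with 44 degrees of freedom and noncentrality d × √45 = 6.708d. The chance of missing the worsening is 1 − power. Section 9.3 calls for an unspecified multiplicity adjustment, so the last column assumes Bonferroni over five signs (0.05/5 = 0.01).

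| d (assumed) | Noncentrality | Missed at 0.05 | Missed at 0.01 |
|---|---|---|---|
| 0.2 | 1.34 | 74% | 90% |
| 0.3 | 2.01 | 50% | 74% |
| 0.5 | 3.35 | 9% | 26% |

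The t-test would usually find a shift of half an SD if unadjusted, but it often misses smaller ones. Adjusting for multiplicity makes a miss more likely, which is the wrong direction if absence of a finding is to be read as reassurance.

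**Whether an equivalence test for staining is feasible at the planned size.** Assumed: two one-sided tests at 0.05 each, true difference zero, normal data, n = 45 (simulated, 400,000 replicates). Power is 68%, 90% and 98% for margins of 0.4, 0.5 and 0.6 SD of the paired difference.

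**Why not simply add equivalence hypotheses for more signs.** If k independent signs must all pass at a 0.5 SD margin, joint power is 0.902^k: 81% for two, 73% for three and 60% for five. Each sign would also need a margin that the documents do not supply.

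Grades are ordinal and may pile up at zero, so all these percentages are guides to order of size only.

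**The case against.** The strongest reply is that the other signs are not ignored. Section 9.3 compares slit lamp findings between lenses, and adverse events are reported under Section 8, so a marked worsening could well be seen. That is correct. What remains is that the comparison is a difference test with no stated consequence for Validation.

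It can also be said that Section 9.3's reference to secondary hypotheses was meant to cover every hypothesis on a secondary endpoint, staining included. That is possible, but Section 9.1 uses the label for vision alone, so the text needs to say so.

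Two stronger readings are tempting, and the documents do not support them.

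- *Two days is too short to judge ocular health.* Every hypothesis in Section 9.1 is already limited to two days of wear. The limit applies equally to all five requirements, and study length is a design choice that Section 4 states openly.
- *Adverse-event codes defined by two weeks or more could not arise in this study.* Code 17 also covers any sign or symptom given therapeutic treatment, with no duration attached. Section 8.2 follows subjects to resolution, and the codes are reporting categories rather than Validation criteria.

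The Appendix 2 scales are not visible in the available text, so which other signs are graded cannot be read. That is not a fault of the plan, but it is a reason not to prescribe particular signs.

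**Conclusion.** The scope mismatch holds. For one of five User Requirements, the hypothesis covers one sign, the analysis section describes no equivalence test for that sign, and the remaining slit lamp findings have no role in the decision. A conclusion of equivalent ocular health would exceed what is tested.

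A reader might infer that a lens which worsened redness or lid signs would still be declared validated. The text does not go that far. Section 1 says the Section 9.1 hypotheses are required, not that they are sufficient. It calls the study supportive evidence for requirements held in a separate design-input document, whose definition of ocular health is not available here.

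The size cannot be given in grading units. The miss rates above rest on 45 completers, normal differences and assumed effect sizes. They show only that non-significance is weak evidence of equivalence. The comfort and vision hypotheses are unaffected. The point should be settled before unmasking.

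**What to change.** 1. Leave the User Requirement as it stands, since it comes from an external document. In Sections 4 and 9.1, and in the Validation conclusion, state that this study's equivalence claim for ocular health is limited to corneal staining over two days of daily wear.
2. In Section 9.3, extend equivalence testing to the staining hypothesis, with a margin fixed before unmasking.
3. For each other slit lamp sign already graded, report the paired Test minus Control difference with a confidence interval, and state that a non-significant t-test will not be read as equivalence.

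The cost is a narrower claim, the work of justifying one margin, and a little more analysis. No added visits, subjects or measurements are needed. Power for the staining test depends on the margin chosen, so it should be calculated once a margin and a plausible SD are available.
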